### 7.7.9 Response based on IWG 2023

Response based on IWG 2023 criteria (see Appendix 11.2 b) at visit 9 will be analyzed only for MDS population. Response assessed in week [REDACTED] will be classified as:

- Overall Response Rate (ORR) = CR (or CR equivalent)\* or PR or CRL or CRh or HI
- or
- No response = Not meeting criteria for CR (or CR equivalent)\* or PR or CRL or CRh or HI.

by these criteria.

### 7.7.10 HRQoL scores

Health-Related Quality of Life (HRQoL) score will be accessed using EORTC QLQ-C30, version 3. This questionnaire contains 30 items with different rating scales. Therefore, Table 4 is used to score:

**Table 4: Scoring the QLQ-C30 v3.0**

	Scale	Number of items	Item range*	Version 3.0 Item numbers	Function scales
Global health status / QoL					
Global health status/QoL (revised) †	QL2	2	6	29, 30	
Functional scales					
Physical functioning (revised) †	PF2	5	3	1 to 5	F
Role functioning (revised) †	RF2	2	3	6, 7	F
Emotional functioning	EF	4	3	21 to 24	F
Cognitive functioning	CF	2	3	20, 25	F
Social functioning	SF	2	3	26, 27	F
Symptom scales / items					
Fatigue	FA	3	3	10, 12, 18	
Nausea and vomiting	NV	2	3	14, 15	
Pain	PA	2	3	9, 19	
Dyspnoea	DY	1	3	8	
Insomnia	SL	1	3	11	
Appetite loss	AP	1	3	13	
Constipation	CO	1	3	16	
Diarrhoea	DI	1	3	17	
Financial difficulties	FI	1	3	28	

\* *Item range* is the difference between the possible maximum and the minimum response to individual items; most items take values from 1 to 4, giving *range* = 3.

† (revised) scales are those that have been changed since version 1.0, and their short names are indicated in this manual by a suffix “2” – for example, PF2.

The scoring of the questionnaire will be based on the manual of the EORTC-QLQ-C30 (<https://www.eortc.org/app/uploads/sites/2/2018/02/SCmanual.pdf>)

Mean score of items belonging to the same scale is computed as Raw Score (RS):

$$RS_i = \frac{I_1 + \dots + I_n}{n}; \quad i = Scale$$

All mean scores will be standardized into a 0 to 100 scale.

For **functional scales** (marked as F in Function scales column), final score ( $S_i$ ) will be:

$$S_i = \left\{ 1 - \frac{(RS_i - 1)}{Item\ range} \right\} \times 100; \quad i = Scale$$

For **symptom scales/items** and **global health status/QoL**, final scores will be:

$$S_i = \left\{ \frac{(RS_i - 1)}{Item\ range} \right\} \times 100; \quad i = Scale$$

If at least half of the items of a scale are not missing, missing values will not be computed in the average calculation. Otherwise, the score will be stated as missing.

#### 7.7.11 Time to Onset and Duration of Adverse Events

##### Time to onset of AEs

The following formula will be used to calculate the time to onset of AEs:

$$\text{Time to onset [days]} = \text{start date} - \text{date of first treatment} + 1$$

This formula can be used analogously whenever the time of onset must be calculated.

##### Duration of AEs

The following formula will be used to calculate the duration of AEs:

$$\text{Duration [days]} = \text{stop date} - \text{start/onset date} + 1$$

This formula can be used analogously whenever the duration must be calculated.

### 7.7.12 Adverse Event and Toxicity Classification

An adverse event will be classified as a treatment emergent adverse event (TEAE) when it occurs only after treatment with IMP has started or is an already present event that worsens either in intensity, frequency during or following the treatment or changed from being not suspected to being suspected following the treatment.

Treatment emergent adverse events will be grouped into related and unrelated TEAEs. All TEAEs that are at least possibly related (Possible related, Probable related, Related) to the treatment or with missing assessment of the relationship will be categorized as related. All other TEAEs will be regarded as unrelated to the treatment.

For the purpose of ranking the severity of an TEAE and the toxicity, the categories will be ordered as following, from lowest to highest severity according to CTCAE v5.0:

- Grade 1 (Mild)
- Grade 2 (Moderate)
- Grade 3 (Severe)
- Grade 4 (Life threatening consequences)
- Grade 5 (Death related to AE)

TEAE occurring before visit [REDACTED] will be accounted for early toxicity.

### 7.7.13 Time to first related TEAE with toxicity of grade 3 or higher

The time to first related TEAE with toxicity of grade 3 or higher (TtFRT) will be measured as the difference between the date of first dose administration and the date of the first occurrence of a TEAE classified as related with severity of grade 3 or higher as defined in section 7.7.12. I.e.:

$$\text{TtFRT [days]} = \min(\text{Date of TEAE where (severity} \geq 3 \text{ and Relationship in (Possible related, Probable related, Related))} - \text{Drug administration date in Visit [REDACTED]}) + 1$$

Otherwise, censoring date will be:

$$\text{TtFRT [days]} = \text{date of last observation} - \text{Drug administration date in Visit [REDACTED]} + 1$$

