9.2.3 Relationship to IMP

All AEs and SAEs must have their relationship to IMP assessed by the investigator who examines and evaluates the study participant based on temporal relationship and clinical judgment. The degree of certainty about causality will be graded using the categories below:

Related – There is clear evidence to suggest a causal relationship, and other possible contributing factors can be ruled out. The clinical event, including an abnormal laboratory test result, occurs in a plausible time relationship to IMP administration and cannot be explained by concurrent disease or other drugs or chemicals. The response to withdrawal of the IMP (dechallenge) should be clinically plausible. The event must be pharmacologically or phenomenologically definitive, with use of a satisfactory rechallenge procedure, if necessary.

Probable Related – There is evidence to suggest a causal relationship, and the influence of other factors is unlikely. The clinical event, including an abnormal laboratory test result, occurs within a reasonable time after administration of the IMP, is unlikely to be attributed to concurrent disease or other drugs or chemicals, and follows a clinically reasonable response on withdrawal (dechallenge). Rechallenge information is not required to fulfill this definition.

Possible Related – There is some evidence to suggest a causal relationship (e.g., the event occurred within a reasonable time after administration of the IMP). However, other factors may have contributed to the event (e.g., the study participant's clinical condition, other concomitant events). Although an AE may rate only as "possibly related" soon after discovery, it can be flagged as requiring more information and later be upgraded to "probably related" or "definitely related", as appropriate.

Unlikely to be related – A clinical event, including an abnormal laboratory test result, whose temporal relationship to IMP administration makes a causal relationship improbable (e.g., the event did not occur within a reasonable time after administration of the IMP) and in which other drugs or chemicals or underlying disease provides plausible explanations (e.g., the participant's clinical condition, other concomitant treatments).

Not Related – The AE is completely independent of IMP administration, and/ or evidence exists that the event is related to another etiology. There must be an alternative, definitive etiology documented by the investigator.

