To minimize the amount of missing data, investigators will be trained on the deleterious effect that missing data have on clinical investigation integrity and credibility and that missing data could diminish the scientific value of all subjects' altruistic contributions. In addition, all data important for study endpoint evaluations will be marked as required within the EDC system, so the investigator or designee will need to explain missing values electronically.

After completion and cleaning of data, the database is locked, and the data exported for statistical analysis.

Entries made in the eCRF and the corresponding entire query communication must be in English language for all participating countries and its trial sites and the monitors.

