## 8.5 Evaluation of Safety Endpoints

Analysis of safety endpoints will be based on the SES. Adverse events will be analyzed by relationship (Possible related, probable related and related will be considered as related to IMP) and severity (Grade 3 or higher according to CTCAE v5.0 will be considered as severe).

All results will be presented by treatment cohort (see 2.7).

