### 8.5.1 Analysis of AEs

The analysis of AEs will be based on the SES. In this trial, only TEAE's (see section 7.7.12) will be analyzed. TEAEs will be classified by system organ class and preferred term using the Medical Dictionary for Regulatory Activities (MedDRA).

An overview of the subjects experienced an TEAE and the number of TEAE will be tabulated. Additionally, TEAE will be summarized by relation to IMP, toxicity (severity), special interest (AESI) and early toxicity.

Individual listings of AEs, SAEs and deaths will be generated.

TEAEs leading to premature discontinuation of study drug or withdrawal from the study will be listed in the same manner.

Table	
14.7.1	TEAEs by SOC and PT, overall
14.7.2	TEAEs by SOC and PT, by relationship
14.7.3	TEAEs by SOC and PT, by toxicity
14.7.4	TEAEs by SOC and PT, by early toxicity
14.7.5	TEAEs by SOC and PT, by special interest
Listing	
16.7.1	Adverse events
16.7.2	Serious adverse events
16.7.3	Adverse Events leading to discontinuation
16.7.4	Death

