### 8.5.2 Time and rate to first related TEAE with toxicity of grade 3 or higher

Time to first related TEAE with toxicity of grade 3 or higher acc. CTCAE v5.0 criteria as defined in section 7.7.13 will be evaluated using Kaplan-Meier method based on the SES. The estimates

obtained are invariably expressed graphically. Median survival time with two-sided 95% confidence intervals (CI) using the complementary log-log transformation method will be tabulated. Survival rate before week ■ (in ■■■■■) and week ■ (in ■■■■■) with exact two-sided 95% confidence interval using the Clopper-Pearson method will be provided.

Table	
14.7.6	Time and rate to first related TEAE with toxicity of grade 3 or higher
Figures	
14.7.6	Time to first related TEAE with toxicity of grade 3 or higher

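### The formula for time to first related grade 3 or higher TEAE, and the relatedness list in SAP 8.5, drop events with missing causality that SAP 7.7.12 counts as related

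*SAP*

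**What the plan says.** Three places in the SAP define what counts as a related TEAE.

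- **SAP 7.7.12** gives the general rule. Related means possibly, probably or definitely related, "or with missing assessment of the relationship will be categorized as related". Everything else is unrelated.
- **SAP 7.7.13** defines the endpoint as the time to the first "TEAE classified as related with severity of grade 3 or higher as defined in section 7.7.12". It then restates this as a formula whose relationship condition is "Relationship in (Possible related, Probable related, Related". A patient with no qualifying event is censored at the last observation.
- **SAP 8.5** introduces the safety analyses, including adverse events by relationship, with the statement "Possible related, probable related and related will be considered as related to IMP". Missing causality is not mentioned.

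Two sets of outputs depend on these texts. SAP 8.5.1 says "TEAE will be summarized by relation to IMP, toxicity (severity), special interest (AESI) and early toxicity", and the by-relationship summary is Table 14.7.2. SAP 8.5.2 takes the time-to-event variable from 7.7.13 for a Kaplan-Meier analysis on the Safety Evaluation Set. It also reports event-free rates at two landmarks "with exact two-sided 95% confidence interval using the Clopper-Pearson method will be provided". Those results go to Table and Figure 14.7.6.

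**The concern.** The formula in 7.7.13 is presented as equivalent to the sentence before it, and it is not. A missing value fails a test of membership in a three-value list, so the formula reverses the conservative rule that 7.7.12 chose for exactly this situation. SAP 8.5 repeats the narrower list, so two of the three texts point a programmer the wrong way. SAP 7.1 adds that missing data are not imputed and makes no exception for causality, which could be read as support for the narrow list.

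The affected variable is listed among the secondary safety endpoints in SAP 6.2.2. It is reported by treatment cohort, and Cohort 2 is dosed more frequently, so severe related toxicity is one of the results a reader will look at. If the choice between the two readings is left until after lock, it could be made with the affected events in view.

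**Working it through.** The plan gives no figure to reproduce, so the check is a comparison of texts followed by illustrations.

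**1. Treatment of one grade 3 or higher TEAE under each text**

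| Recorded relationship | SAP 7.7.12 | SAP 7.7.13 formula | SAP 8.5 list |
|---|---|---|---|
| Related, probable or possible | related | counted | related |
| Unlikely or not related | unrelated | not counted | not listed |
| Missing | **related** | **not counted** | **not listed** |

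The texts agree in every row except the last.

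**2. Direction of the error.** The formula takes the minimum date over a subset of the events that 7.7.12 admits. A minimum over a subset cannot be earlier than the minimum over the full set. The derived time therefore stays the same, becomes longer, or turns from an event into a censored time. It never becomes shorter.

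**3. Delay (hypothetical patient).** Suppose a grade 3 TEAE with missing causality occurs on day 20 and a possibly related grade 3 TEAE on day 60.
- Under 7.7.12: min(20, 60) = day 20.
- Under the formula: day 60, which is 60 − 20 = 40 days later.
- If the day-20 event were the only one, the patient would be an event at day 20 under 7.7.12 and censored at last observation under the formula.

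**4. Rate (assumed cohort size).** Final cohort sizes are not legible in the documents, so n is an assumption. One patient whose only grade 3 or higher TEAE lacks causality changes the crude proportion by 1/n:
- n = 10: 1/10 = 10.0 points
- n = 20: 1/20 = 5.0 points
- n = 22: 1/22 = 4.5 points

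**5. The same on the event-free scale of SAP 8.5.2.** Take n = 20, the affected event before the landmark, and no earlier censoring. The event counts are invented for illustration. Exact (Clopper-Pearson) 95% intervals are:
- Formula as written, 5 events: 15/20 = 75.0% (50.9 to 91.3)
- Rule in 7.7.12, 6 events: 14/20 = 70.0% (45.7 to 88.1)

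**6. No missing causality at lock.** The last row of the table in step 1 is empty, and the two definitions give identical results.

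**The case against.** The best defence is that the SAP already answers the question. SAP 7.7.12 is the only text that addresses missing causality, and the wording of 7.7.13 points to it, so the formula is an incomplete restatement and not a rival rule. SAP 8.5 omits missing causality without saying that it means unrelated. A single related flag derived from 7.7.12 could feed both outputs, and SAP 3.1 requires a second programmer to validate each program.

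The trigger should also be uncommon. Protocol 9.2.3 states "All AEs and SAEs must have their relationship to IMP assessed by the investigator", and Protocol 11.2 says "all data important for study endpoint evaluations will be marked as required within the EDC system". An affected event would still appear in Tables 14.7.1 and 14.7.3 and in Listing 16.7.1. Protocol 10.1 makes every analysis exploratory, and no decision in the plan is tied to Table 14.7.6.

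Most of this stands as an argument about likelihood and size. It does not remove the contradiction. Validation catches the mismatch only if the two programmers read the SAP differently. If both code the formula, the outputs agree and the error passes. A required field does not guarantee a value either, because Protocol 11.2 allows a missing value to be explained, and 7.7.12 itself plans for missing causality. The point about 8.5 is fair: the effect on Table 14.7.2 is possible, not certain.

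**Conclusion.** The concern holds. The 7.7.13 formula contradicts the definition it cites, and the 8.5 list omits the same category. Followed literally, both depart from 7.7.12, always towards less or later related severe toxicity.

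The practical effect is likely small. It requires at least one TEAE with missing causality at lock (grade 3 or higher for Table 14.7.6), and a program written from the formula or the 8.5 list instead of from 7.7.12. Under those conditions one patient can move a cohort's rate by about 4.5 to 10 points for assumed cohort sizes of 22 down to 10. In the n = 20 illustration the two intervals overlap almost entirely. Nothing in the documents shows how many events, if any, lack causality. The correction is worth making because the endpoint is a listed secondary safety measure and the remedy costs almost nothing.

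**What to change.** - **SAP 7.7.13:** extend the relationship condition in the formula so that it admits the three listed categories or a missing relationship.
- **SAP 8.5:** add missing relationship to the categories treated as related, so that Tables 14.7.2 and 14.7.6 both follow 7.7.12.

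An equivalent route is to derive one related flag from 7.7.12 and refer to it in both places. A short note in SAP 7.1 that this rule is an exception to the no-imputation statement would remove the remaining ambiguity.

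The cost is two short SAP edits, plus the optional note, and one changed program condition. No new data are needed and the design is unaffected. The only downside is that the reported rate of related toxicity may rise slightly, which is what 7.7.12 intends. The edits should be made before database lock.

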## 8. Statistical Analysis Methods

### 8.1 Descriptive Statistics

The default summary statistics for quantitative variables will be the number of non-missing observations (n) and the number of missing observations (miss) as well as arithmetic mean, standard deviation (STD), minimum (min), median, and maximum (max).

For categorical variables, the number (n) and percentage (%) of subjects per category will be the default summary presentation, and, if applicable, the number of missing values is provided in a “missing” category. For the number of missing values, all subjects in the respective study population will be counted. Percentages will be calculated using a denominator of all subjects in a specified population with non-missing data. If necessary, the denominator will be specified in a footnote to the tables for clarification.

Visit related descriptive statistics will be provided only for visits with more than 5 non-missing observations. Results from visits with 5 or less non-missing observation will be only listed.

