2.3 Study endpoints

2.3.1 Primary endpoint

The primary endpoint of the study is defined as overall hematological response rate as assessed in [REDACTED] of treatment with imetelstat.

All patients with one of the following responses assessed by samples and procedures taken/carried out at [REDACTED] are defined as responders (assessed through the combined response criteria for MDS and AML used in this trial (see Appendix III a), section 16.3):

[1] CR, CRi, PR as defined in Appendix III a)

[2] Hematologic improvement (for one or several lines) as defined in Appendix III a)

Response rate is calculated as follows: number of responders divided by the number of all patients of the analysis set. Patients for whom the overall hematologic response cannot be determined will be considered as treatment failures.

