## 4. Analysis Sets and Subgroups

### 4.1 Analysis Sets

#### 4.1.1 Full Analysis Set (FAS)

The Full Analysis Set (FAS) consists of all patients who received at least one dose of study drug and fulfilled the inclusion criteria. The FAS is the primary dataset for analysis.

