#### 4.1.2 Per Protocol Set (PPS)

The Per Protocol Set (PPS) will be defined as the subset of patients of the FAS that reached study week [REDACTED] and who have no major protocol deviations as to be determined on a per-subject basis immediately before data base lock.

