## 6.2 Endpoints and Related Variables

### 6.2.1 Primary Endpoint

Objective	Endpoint
To assess the efficacy of imetelstat for the treatment of AML and MDS patients failing or being refractory to first line hypomethylating agent (HMA)-based treatment	Overall hematological response rate as assessed in week ████████ of treatment with imetelstat using the combined response assessment criteria for MDS and AML (see Appendix 11.2 for more details). The main analysis will be based on the eCRF item “Is the subject classified to be a Responder according to protocol?” (RS_DSRESP).

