Not evaluable	All registered/randomly assigned patients should be reported in the denominator of response assessment analyses in line with the intention-to-treat principle. This category may include patients yet to have a response assessment, suffering early death, exiting the study early, or those with a technically suboptimal BM sample precluding assessment.
Cytogenetic response¶¶	
 
Complete: disappearance of the chromosomal abnormality without appearance of new ones.
 
Partial: <math>\geq 50\%</math> reduction of the chromosomal abnormality.
 

Progressive disease (PD)	
Fulfilling any of the criteria below: #, **, ††
 
 
Disease progression by blasts: <math>\geq 50\%</math> relative increase in blasts and absolute increase of blast percentage by at least 5% from pretreatment sample taken before current line of therapy
 
Disease progression by worsening cytopenia: new, repeated (more than once and separated by <math>\geq 7</math> days) need for RBC or platelet transfusions within 8 weeks, not related to acute intercurrent illness (eg, sepsis, gastrointestinal
 

	
tract bleed) or treatment effect, in the absence of HI of at least one other blood lineage as defined above
 
 
Progression to AML: <math>\geq 50\%</math> increase in blasts from baseline assessment to <math>\geq 20\%</math> blasts.
 

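### Best overall response and IWG 2023 response are reported on non-missing data only, and the PPS rate is conditional on reaching the endpoint week; the primary FAS rate is protected

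*SAP*

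**What the plan says.** **General rule.** SAP 8.1 governs categorical tables: "Percentages will be calculated using a denominator of all subjects in a specified population with non-missing data". A count of missing values is shown where applicable, and the denominator may be footnoted.

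**Primary endpoint.** Protocol 2.3.1 defines the rate as "number of responders divided by the number of all patients of the analysis set" and adds: "Patients for whom the overall hematologic response cannot be determined will be considered as treatment failures". SAP 7.7.4 repeats the failure rule and SAP 8.3 refers to it. SAP 4.1.1 states: "The FAS is the primary dataset for analysis"; the FAS needs one dose and fulfilled inclusion criteria, with no condition on reaching a visit. SAP 6.2.1 names the data source: "The main analysis will be based on the eCRF item" that asks whether the subject is a responder according to protocol.

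**Best overall response.** SAP 8.4.3 refers to the methods of section 8.1. SAP 7.7.8 gives a response hierarchy but no rule for patients without an assessment.

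**IWG 2023 response, MDS only.** SAP 8.4.4 uses the descriptive methods set out earlier in the SAP. SAP 7.7.9 gives two outcomes at visit 9, response or no response. SAP Appendix 2 b), however, says: "All registered/randomly assigned patients should be reported in the denominator of response assessment analyses in line with the intention-to-treat principle". It names early death and early exit among the reasons for being not evaluable.

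**PPS.** SAP 4.1.2, like protocol 10.2.2, defines it as the "subset of patients of the FAS that reached study week" in question (number blacked out) without major deviations. SAP 7.3 makes a subject's own early termination a reason for exclusion, and lists a primary-endpoint assessment not performed among possible critical deviations. Protocol 10.8.1 repeats the primary analysis on the PPS; SAP 8.3 does so only if the sets differ by more than 10%.

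**The concern.** In this population a patient without a response assessment has usually died, progressed or stopped treatment. Removing such patients from a response denominator removes failures, so the percentage rises without any additional response.

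The PPS has the same problem in another form. Protocol 5.1.3, 7.1 and 8.1.4 end treatment when progression is seen at the early assessment, before the primary-endpoint visit. A set that requires reaching the endpoint week can therefore exclude patients because the treatment failed while the protocol was followed. The failure rule of protocol 2.3.1 cannot restore patients who are no longer in the set.

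At stake is how the secondary and PPS percentages are read. Set beside the 5% and 20% rates of protocol 10.3, they would look better than the all-patient rate for reasons unrelated to drug activity. Under the SAP's 10% trigger, the PPS table appears only when the difference between the sets is appreciable.

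**Working it through.** **Step 1. Which denominator applies**

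| Result | Governing text | Patients with no assessment |
|---|---|---|
| Primary, FAS | Protocol 2.3.1, SAP 7.7.4 | Stay in, as failures |
| Primary, PPS | SAP 4.1.2 and 7.3 | Can leave the set before the failure rule acts |
| Best overall response | SAP 8.4.3, which invokes 8.1 | Drop out if never assessed |
| IWG 2023 | SAP 8.4.4, hence 8.1; Appendix 2 b) says otherwise | Drop out if no visit 9 assessment; in conflict with the appendix |

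**Step 2. Size of the distortion.** Let x patients respond out of N, and let a share m be missing or excluded, none of them responders. The reported rate is x / [N(1 − m)] against x / N, a ratio of 1 / (1 − m). The plan does not give m for these tables. Its only attrition figure is the loss to follow-up of about 10% in protocol 10.3, which gives 1 / 0.90 = 1.11.

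**Step 3. Share dying before each visit (assumption).** Protocol 1.1.1 gives a median survival of 4 to 5.6 months for higher-risk MDS progressing on HMA. SAP 8.3 places visit 5 in week 9 and visit 9 in week 17; protocol 10.9.3 confirms week 17. These weeks begin 8 and 16 weeks after the first dose: 56 / 30.4 = 1.84 months and 112 / 30.4 = 3.68 months. With a constant hazard, m = 1 − 0.5^(t / median).

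| Visit | Median 5.6 months | Median 4 months | Ratio 1 / (1 − m) |
|---|---|---|---|
| Week 9 (best overall response) | 1 − 0.5^(1.84/5.6) = 20% | 1 − 0.5^(1.84/4) = 27% | 1.26 to 1.38 |
| Week 17 (PPS, IWG 2023) | 1 − 0.5^(3.68/5.6) = 37% | 1 − 0.5^(3.68/4) = 47% | 1.58 to 1.89 |

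Only deaths are counted. Early progression and other exits before visit 9 would add to the week 17 share.

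**Step 4. Illustration.** Take N = 20 and two responders, 2/20 = 10%. At week 17, 20 × 0.63 = 12.7 to 20 × 0.53 = 10.6 patients remain, or about 13 to 11: 2/13 = 15.4% and 2/11 = 18.2%. For best overall response, 10% × 1.26 = 12.6% and 10% × 1.38 = 13.8%. N and the responder count are chosen for illustration; actual cohort sizes are largely blacked out.

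**Step 5. Wider range.** For m from 10% to 50% the ratio runs from 1.11 to 2.0, so 4/20 = 20% would read as 22.2% to 40.0%. With no responders the rate is 0% on any denominator. Only the upper limit of the exact 90% interval moves, for example from 13.9% (0/20) to 19.3% (0/14).

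**The case against.** A reader might infer that the primary response rate itself is inflated. The documents do not support this. SAP 8.1 is a default, and the endpoint-specific rule in protocol 2.3.1 and SAP 7.7.4 governs. Applied as written, the FAS rate is not inflated at all.

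A reader might also infer that the responder item in the eCRF is blank after early death and that the SAS procedure drops it. Nothing in the documents shows the item to be blank. Protocol 11.2 has endpoint data marked as required, and the SAS text is offered only as pseudo code. What stands is a gap: SAP 7.1 rules out imputation, and no step in SAP 8.3 sets a blank to non-responder.

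For best overall response, a patient with progression at visit 5 has a recorded category and stays in the denominator. The week 17 figures therefore do not apply to it. Only patients never assessed are lost.

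For IWG 2023, the appendix offers a not-evaluable category, and a programmer who used it would get the right denominator. But SAP 7.7.9 lists only two outcomes and 8.4.4 points to the default, so the outcome depends on which text is followed.

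The PPS is supportive, its exclusions are listed, and protocol 10.1 makes all analyses exploratory. This limits the consequence but does not change what the PPS rate estimates. Week 17 for the PPS is an inference from visit 9. Read literally, a patient in follow-up at that week might also count as having reached it, though SAP 7.3 could still remove that patient because the endpoint assessment was not done.

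The survival figures are for higher-risk MDS, while the trial also enrols AML and HMA-intolerant patients. The SAP document history reports no responders at the interim analysis, so any inflation of a rate matters mainly for cohort 2.

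**Conclusion.** The concern holds for three results and not for the main one. The primary FAS rate is correctly defined and needs only a clarifying line for programming. Best overall response falls under a non-missing denominator with no failure rule. IWG 2023 response falls under the same default against the SAP's own appendix. The PPS rate is conditional on reaching the endpoint week, so it should not be set against the 5% and 20% reference rates.

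The likely inflation is about 1.6 to 1.9 times for PPS and IWG 2023 rates and about 1.3 to 1.4 times for best overall response, provided at least one patient responds. These sizes rest on a constant hazard, on a median survival quoted for only part of the population, on deaths alone, and on the PPS week being that of visit 9. The direction does not depend on them: whenever there is a responder and non-responders are removed, the rate rises.

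**What to change.** - **SAP 8.4.3 and 8.4.4:** as a stated exception to 8.1, use all FAS patients as the denominator (all MDS patients of the FAS for IWG 2023), with a not-evaluable row counted as non-response. This brings 7.7.9 and 8.4.4 into line with Appendix 2 b).
- **SAP 8.3:** state that the analysed flag is derived by 7.7.4 for every FAS patient, and that an undetermined response or blank eCRF item is set to non-responder.
- **PPS, one of two options:** (a) label the rate as conditional on reaching the endpoint visit and not comparable with the 5% and 20% rates; or (b) keep patients who stopped earlier for progression, death, toxicity or lack of efficacy as non-responders. Option (b) also needs SAP 4.1.2, SAP 7.3 and protocol 10.2.2 aligned. Removing the week condition alone is not enough, because the exclusions in SAP 7.3 could take out the same patients.

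The cost is wording, plus a line in the protocol under option (b). No new data are needed, and SAP 2.10 allows SAP updates that are finalized before database lock. The downside is that the secondary rates, and the PPS rate under option (b), become less favourable.
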